| Study Manager | [REDACTED] | This document is signed electronically in the eTMF system | This document is dated electronically in the eTMF system |

INVESTIGATOR SIGNATURE PAGE

| | |
|-----------------------------|--|
| Investigator | [name] Dermatologist [name] |
| Investigational Site | EUROFINS EVIC PRODUCT TESTING ROMANIA S.R.L. [name] |

I have read this protocol and agree to conduct this study in accordance with all stipulations of the protocol and in compliance with all applicable Good Clinical Practices and regulations.

Signature of Investigator

Date

SUMMARY

| | |
|-----------------------------|--|
| Protocol Number: | MPS-17IPVSS02 |
| Protocol Title: | A Randomized, Single-Center, Partially Blinded, Evaluation of the Time-Dependent Antimicrobial Effectiveness of Swabsticks Impregnated with 2% (w/v) Chlorhexidine Gluconate in 70% (v/v) Isopropyl Alcohol in Healthy Volunteers |
| Planned Sample Size: | This study will include a minimum of 516 evaluable subjects to achieve 280 evaluable sites per anatomical location for the investigational product (IP), active control (AC), and negative control (NC) and 192 evaluable sites per anatomical location for the reference standard (RS). |
| Study Design: | This single site study is a randomized, controlled, partially-blinded design enrolling a minimum of 516 healthy volunteers, where each subject will receive two of the planned study products on the product application sites of the abdomen and/or groin. |
| Study Methodology: | ASTM Standard Test Method E1173-15 |
| Study Population: | 
Healthy male and female volunteers, 18 years of age or older.
 
Screening Day bacterial count requirements of at least 3.20 log₁₀/cm² on the abdomen and 5.50 log₁₀/cm², on the groin.
 
Product Application Day baseline bacterial count requirements are in the range of 3.20 to 6.00 log₁₀/cm², inclusive, on the abdomen or 5.50 to 7.50 log₁₀/cm², inclusive, on the groin.
 |
| Objectives: | 
To demonstrate the antimicrobial activity of the Investigational Product (IP) administered as a single Swabstick application by comparing counts of resident skin microbes, obtained after IP application to intact skin of the abdomen and groin, to counts obtained prior to application.
 
In this study, the antimicrobial activity of the IP will be investigated according to established testing requirements described by Health Canada (HC) and the US FDA.
 
Efficacy Objectives according to HC testing requirements
 
Primary Objective: To demonstrate the immediate and persistent antimicrobial activity of a single Swabstick impregnated with 2% (w/v) chlorhexidine gluconate in 70% (v/v) isopropyl alcohol at 30 seconds and 6 hours post product application.
 
Exploratory Objectives: 1) To evaluate the log₁₀ reductions from baseline for the IP and RS at each anatomical site at 10 minutes post product application. 2) To determine if the 30-second, 10 minutes and 6 hour log₁₀ reductions on the abdomen and groin for the IP are not statistically worse than those for 60% v/v 1-propanol post product application.
 |

| | |
|--|--|
| 
Protocol Number:
 | 
MPS-17IPVSS02
 |
| | 
Efficacy Objectives according to FDA testing requirements
 
Primary Objectives: 1) To demonstrate superior antimicrobial activity of the IP, a single Swabstick impregnated with 2% (w/v) chlorhexidine gluconate in 70% (v/v) isopropyl alcohol, to a negative control (NC) of 0.9% normal saline and the non-inferiority of the IP to an active control (AC) at the immediate time point of 10 minutes on the abdomen and groin. 2) To demonstrate persistence of the IP at 6 hours post product application on the abdomen and the groin.
 
Secondary Objective: To demonstrate superior antimicrobial activity of the IP, a single Swabstick impregnated with 2% (w/v) chlorhexidine gluconate in 70% (v/v) isopropyl alcohol, to a negative control (NC) of 0.9% normal saline and the non-inferiority of the IP to an active control (AC) at 30 seconds post product application on the abdomen.
 
Exploratory Objectives: 1) To evaluate the log₁₀ reductions from baseline for the IP, AC and NC at each anatomical site at 30 seconds, 10 minutes, and 6 hours post product application. 2) To evaluate the amount of product applied (g) to each anatomical site for each product.
 
Safety Objectives: To evaluate safety using skin irritation scores and the incidence of adverse events reported during the study.
 |
| 
Study Endpoints and Acceptance Criteria:
 | 
Efficacy Endpoints: The primary endpoint will be log₁₀ CFU/cm² of skin before and after product application at 30 seconds, 10 minutes and 6 hours on the abdomen and groin.
 
Acceptance Criteria according to HC analysis: For the IP:
 
 1. Immediate effectiveness is at least a 2-log₁₀ CFU/cm² reduction from baseline skin flora counts for the abdomen at 30 seconds. 2. Immediate effectiveness is at least a 3-log₁₀ CFU/cm² reduction from baseline skin flora counts for the groin at 30 seconds. 3. Persistence effectiveness is at least a 2- log₁₀ CFU/cm² reduction from baseline skin flora counts for the abdomen at 6 hours. 4. Persistence effectiveness is at least a 3- log₁₀ CFU/cm² reduction from baseline skin flora counts for the groin at 6 hours. 
The reference standard, 60% v/v 1-Propanol, should meet the same efficacy standards as the investigational product.
 |

| | |
|--------------------------------|--|
| 
Protocol Number:
 | 
MPS-17IPVSS02
 |
| | 
Acceptance Criteria according to FDA analysis:
 
For assessment of the primary objectives (i.e., immediate activity at 10 minutes post application on the abdomen and groin):
 
 1. A non-inferiority criterion with a 0.5 log₁₀ margin will be implemented for the average treatment effect (ATE) of the IP compared to the AC (i.e., the upper two-sided 95% confidence bound of the post-product application bacterial load corrected for pre-product application bacterial load of the IP – AC should be less than 0.5 log₁₀). 2. A 1.2 log₁₀ superiority criterion will be implemented for the ATE of the IP compared to the NC (i.e., the lower two-sided 95% confidence bound of the post-product application bacterial load corrected for pre-product application bacterial load of the NC – IP should be greater than 1.2 log₁₀). 
Persistence of efficacy will be defined at 6 hours post-application as having ≥0 log₁₀ reduction from baseline bacterial load. No inferential analysis will be performed on the 6 hour time point data.
 
For assessment of the secondary objective (i.e., antimicrobial activity at 30 seconds post application on the abdomen):
 
 1. A non-inferiority criterion with a 0.5 log₁₀ margin will be implemented for the ATE of the IP compared to the AC (i.e., the upper two-sided 95% confidence bound of the post-product application bacterial load corrected for pre-product application bacterial load of the IP – AC should be less than 0.5 log₁₀). 2. A 1.2 log₁₀ superiority criterion will be implemented for the ATE of the IP compared to the NC (i.e., the lower two-sided 95% confidence bound of the post-product application bacterial load corrected for pre-product application bacterial load of the NC – IP should be greater than 1.2 log₁₀). 
Assessment of the primary endpoints (i.e., antimicrobial activity at 10 minutes post application on both abdomen and groin) and secondary endpoints (i.e., antimicrobial activity at 30 seconds post application on the abdomen) will follow a gatekeeping procedure: the secondary endpoints (i.e., antimicrobial activity at 30 seconds post application on the abdomen) will be evaluated only when the assessment of the primary endpoints (i.e., immediate activity at 10 minutes post application on the abdomen and groin) passes non-inferiority and superiority criteria on both abdomen and groin.
 
Safety endpoints: Safety will be evaluated using skin irritation scores and the incidence of AEs reported during the study.
 |

| Protocol Number: | MPS-17IPVSS02 | | | | | | | | | | | | | | | | | | | | | | | | | | | | | | | | | | | | | | | | | | | | |
|-------------------------|---|------------------|------------|----------------------------------|----------------|-----------------|------------------|----------|------------------|----|---------|------------|------------|----------------------------------|-------|-----------|-----------|---------------------------------|----|---------|------------|------------|----------------------------------|-------|-----------|-----------|---------------------------------|----|---------|------------|------------|----------------------------------|-------|-----------|-----------|---------------------------------|----|---------|------------|------------|----------------------------------|-------|-----------|-----------|---------------------------------|
| Study Products: | 
Investigational Products (IP): Single Swabstick impregnated with 1.75 mL of 2% (w/v) chlorhexidine gluconate (CHG) in 70% (v/v) isopropyl alcohol (thermally treated)
 
Reference Standard (RS): 1.75 mL of 60% (v/v) 1-propanol applied with a single Swabstick
 
Active Control (AC): Chloraprep® SEPP® clear applicator-2% (w/v) chlorhexidine gluconate in 70% (v/v) isopropyl alcohol
 
Negative Control (NC): 1.75 mL 0.9% normal saline applied with a single Swabstick
 
Study Products, Anatomical Sites Evaluated, Application and Dry Times, and Coverage Areas:
 
  
 Study Products	Anatomical Site	Application Time	Dry Time	Area of Coverage	
   
 IP	Abdomen	30 seconds	30 seconds	2.5" x 2.5" (6.4 cm x 6.4 cm)	
 
 Groin	2 minutes	1 minutes	1.3" x 5" (3.3 cm x 12.7 cm)	
 
 AC	Abdomen	30 seconds	30 seconds	2.5" x 2.5" (6.4 cm x 6.4 cm)	
 
 Groin	2 minutes	1 minutes	1.3" x 5" (3.3 cm x 12.7 cm)	
 
 NC	Abdomen	30 seconds	30 seconds	2.5" x 2.5" (6.4 cm x 6.4 cm)	
 
 Groin	2 minutes	1 minutes	1.3" x 5" (3.3 cm x 12.7 cm)	
 
 RS	Abdomen	30 seconds	30 seconds	2.5" x 2.5" (6.4 cm x 6.4 cm)	
 
 Groin	2 minutes	1 minutes	1.3" x 5" (3.3 cm x 12.7 cm)	
  
 | | | | Study Products | Anatomical Site | Application Time | Dry Time | Area of Coverage | IP | Abdomen | 30 seconds | 30 seconds | 2.5" x 2.5" (6.4 cm x 6.4 cm) | Groin | 2 minutes | 1 minutes | 1.3" x 5" (3.3 cm x 12.7 cm) | AC | Abdomen | 30 seconds | 30 seconds | 2.5" x 2.5" (6.4 cm x 6.4 cm) | Groin | 2 minutes | 1 minutes | 1.3" x 5" (3.3 cm x 12.7 cm) | NC | Abdomen | 30 seconds | 30 seconds | 2.5" x 2.5" (6.4 cm x 6.4 cm) | Groin | 2 minutes | 1 minutes | 1.3" x 5" (3.3 cm x 12.7 cm) | RS | Abdomen | 30 seconds | 30 seconds | 2.5" x 2.5" (6.4 cm x 6.4 cm) | Groin | 2 minutes | 1 minutes | 1.3" x 5" (3.3 cm x 12.7 cm) |
| Study Products | Anatomical Site | Application Time | Dry Time | Area of Coverage | | | | | | | | | | | | | | | | | | | | | | | | | | | | | | | | | | | | | | | | | |
| IP | Abdomen | 30 seconds | 30 seconds | 2.5" x 2.5" (6.4 cm x 6.4 cm) | | | | | | | | | | | | | | | | | | | | | | | | | | | | | | | | | | | | | | | | | |
| | Groin | 2 minutes | 1 minutes | 1.3" x 5" (3.3 cm x 12.7 cm) | | | | | | | | | | | | | | | | | | | | | | | | | | | | | | | | | | | | | | | | | |
| AC | Abdomen | 30 seconds | 30 seconds | 2.5" x 2.5" (6.4 cm x 6.4 cm) | | | | | | | | | | | | | | | | | | | | | | | | | | | | | | | | | | | | | | | | | |
| | Groin | 2 minutes | 1 minutes | 1.3" x 5" (3.3 cm x 12.7 cm) | | | | | | | | | | | | | | | | | | | | | | | | | | | | | | | | | | | | | | | | | |
| NC | Abdomen | 30 seconds | 30 seconds | 2.5" x 2.5" (6.4 cm x 6.4 cm) | | | | | | | | | | | | | | | | | | | | | | | | | | | | | | | | | | | | | | | | | |
| | Groin | 2 minutes | 1 minutes | 1.3" x 5" (3.3 cm x 12.7 cm) | | | | | | | | | | | | | | | | | | | | | | | | | | | | | | | | | | | | | | | | | |
| RS | Abdomen | 30 seconds | 30 seconds | 2.5" x 2.5" (6.4 cm x 6.4 cm) | | | | | | | | | | | | | | | | | | | | | | | | | | | | | | | | | | | | | | | | | |
| | Groin | 2 minutes | 1 minutes | 1.3" x 5" (3.3 cm x 12.7 cm) | | | | | | | | | | | | | | | | | | | | | | | | | | | | | | | | | | | | | | | | | |

| | |
|------------------------------------|---|
| 
Statistical Methods:
 | 
The full intent-to-treat (ITT) data set (all randomized subjects that received study product) will be used for the safety analysis.
 
A modified intent-to-treat (mITT) data set will be used for efficacy analyses for both the FDA and HC analyses. Data included in the mITT data set is evaluated for each anatomical site (left and right for the groin and abdomen). For each anatomical site, if the Product Application Day baseline bacterial count is in the range of 3.20 to 6.00 \log_{10}/cm^2, inclusive, on the abdomen or 5.50 to 7.50 \log_{10}/cm^2, inclusive, on the groin, then the data from that anatomical site are included in the mITT data set.
 
Supportive analysis for both the FDA and HC analyses will be performed on the per-protocol population (PP). The PP data set will include evaluable product application sites from the mITT data set that adhere to defined assessments and procedures in the protocol central to patient enrollment, safety, rights or wellbeing, as well as the completeness, accuracy and reliability of study data. Additional details on qualification for the PP data set are outlined in the Statistical Analysis Plan (SAP).
 
A summary table will present \log_{10} CFU/cm² for each study product on each anatomical site at each time point.
 
An analysis of variance (ANOVA) of the baseline \log_{10} CFU/cm² values will be performed separately for abdomen and groin to determine whether the randomization produced study product arms with similar baseline CFU/cm² values.
 
Safety Analysis: The statistical significance of differences in skin irritation between the study products at each post application sampling time will be evaluated by Fisher’s exact test on skin irritation data summarized for safety analysis as follows: any reaction above a zero (no reaction) on the skin irritation rating scale for any category (erythema, edema, rash, and dryness) will be considered a positive signal for that substance. If Fisher’s exact test shows statistically significant skin irritation between the study products, follow-up analyses will be conducted to determine how the reactions differ. No statistical analysis will be performed on the incidence of AEs.
 
HC Efficacy Analyses
 
HC Primary Analysis: \log_{10} CFU/cm² changes from baseline will be calculated separately for each subject, each of the four sites (left and right for the abdomen and groin), and each post-product application sampling time by taking the baseline \log_{10} CFU/cm² values and then subtracting the \log_{10} CFU/cm² values for the samples taken after baseline. The mean \log_{10} CFU/cm² changes from baseline will be calculated separately for the IP and the RS, at each anatomical site (abdomen and groin), and at each post-product application sampling time point (30 seconds and 6 hours).
 
The following descriptive statistics for \log_{10} CFU/cm² reductions will be computed for the IP and RS, grouped by anatomical site and each post application sampling time point (30 seconds and 6 hours): mean, median, standard deviation, minimum, maximum, and count. The 95% confidence intervals (two-sided) will be calculated for the observed log reductions for the IP and RS at each time point on each anatomical area using one-sample t-test.
 |
|------------------------------------|---|

| | |
|--|---|
| | 
The goal for the IP is that the mean \log_{10} reduction of all four primary objectives meets the following criteria:
 
 1. The lower limit of the 95% confidence interval (two-sided) of mean log reduction at 30 seconds will be greater than or equal to 2 for the abdomen. 2. The lower limit of the 95% confidence interval (two-sided) of mean log reduction at 30 seconds will be greater than or equal to 3 for the groin. 3. The lower limit of the 95% confidence interval (two-sided) of mean log reduction at 6 hours will be greater than or equal to 2 for the abdomen. 4. The lower limit of the 95% confidence interval (two-sided) of mean log reduction at 6 hours will be greater than or equal to 3 for the groin 
The HC testing requirements will only be considered met when and only when all four primary objectives pass HC analysis acceptance criteria. No multiplicity adjustment is required.
 
The RS should meet the same efficacy standards as the IP.
 
HC Exploratory Analysis: 1) The following descriptive statistics for \log_{10} CFU/cm² reductions will be computed for the IP and RS, grouped by anatomical site and each post application sampling for the 10 minute time point: mean, median, standard deviation, minimum, maximum, and count. The 95% confidence intervals (two-sided) will be calculated for the observed log reductions for the IP and RS at the 10 minute time point on each anatomical area.
 
2) \log_{10} CFU/cm² reductions at 30 seconds, 10 minutes, and 6 hours on the abdomen and the groin for the IP will be compared to the RS using two-sample t-test.
 
FDA Efficacy Analyses
 
FDA Primary Analysis: A linear regression model for each body site (abdomen and groin) will be used for primary analysis of efficacy at 10 minutes. In the model, the response is the post-product application bacterial counts at 10 minutes and predictors are the study products as a fixed effect and the pre-product application bacterial loads as a covariate. The ATE corrected for pre-product application bacterial loads will be estimated from the model and compared to both non-inferiority and superiority criteria.
 
The FDA testing requirements for the primary analysis will only be considered met when and only when all four primary objectives (10 minutes for both abdomen and groin) pass FDA analysis acceptance criteria, no multiplicity adjustment is required.
 
To evaluate the persistent antimicrobial properties of a single Swabstick impregnated with 2% (w/v) chlorhexidine gluconate in 70% (v/v) isopropyl alcohol, \log_{10} bacterial counts at 6 hours post product application for each product application site will be converted to a binary (yes or no) success measure with success defined as having skin flora counts that are less than or equal to the baseline skin flora counts. Responder rates at 6 hours post product application will be summarized descriptively for each
 |
|--|---|

| | |
|--|---|
| | 
product on each body site. No inferential analysis will be performed on the 6 hour time point data.
 
FDA Secondary Analysis: The secondary objectives will be evaluated only when the four co-primary objectives pass both non-inferiority and superiority criteria. A linear regression model for the abdomen will be used for a secondary analysis of efficacy at 30 seconds. In the model, the response is the post-product application bacterial counts at 30 seconds and predictors are the study products as a fixed effect and the pre-product application bacterial loads as a covariate. The ATE corrected for pre-product application bacterial loads will be estimated from the model and compared to both non-inferiority and superiority criteria.
 
FDA Exploratory Analyses: The following descriptive statistics for \log_{10} CFU/cm² reductions will be computed for the IP, AC and NC at each anatomical site at 30 seconds, 10 minutes, and 6 hours post product application: mean, median, standard deviation, minimum, maximum, and count.
 
Product weight expression will be calculated as product weight prior to product application (g) – product weight post-product application (g). The following descriptive statistics for expression weight will be computed for each product at each anatomical site: mean, median, standard deviation, minimum, maximum, and count.
 |
|--|---|

Table of Contents

SUMMARY 4

LIST OF ABBREVIATIONS AND DEFINITION OF TERMS 14

1.0 INTRODUCTION 15

2.0 OBJECTIVES 15

 2.1 Safety Objectives.....15

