3.3 Product Application Allocation and Methods to Reduce Bias

3.3.1 Randomization

The randomization scheme for the study will be provided by the Sponsor. A sufficient number of subjects will be recruited and newly randomized to meet the minimum number of evaluable product application sites per study product arm, preserving the randomization assignment. The number of evaluable product application sites per study product arm per anatomical area will be monitored to determine additional subject enrollment and randomization to meet the required evaluable sample size. Subjects who fail to meet Product Application Day baselines will not be replaced. Additional subjects will be randomized to account for product application day failures.

Subjects will be randomized to study product arms using the following block design:

Study Product Balance

Each subject will receive two different study products, one on the right side of the body and one on the left. Therefore, there are six possible study product combinations: A-B, A-C, A-D, B-C, B-D and C-D.

A minimum of 516 evaluable subjects will be required to achieve a total of a minimum of 192 evaluable product application sites for groin and abdominal regions for 60% (v/v) 1-propanol (RS) and 280 evaluable product application sites for groin and abdominal regions for the other three study product arms. Due to the imbalance of the sample size between RS and other products, RS cannot be blinded. Assuming the treatment code for RS is B and all the other three products are either A, C or D, within each small block [i.e., every 129 (516/4) evaluable subjects randomized], number of subjects who receive each product combination is shown below. With 4 blocks in total (i.e., 516 evaluable subjects), the minimum of 192 evaluable product application sites for groin and abdominal regions for 60% (v/v) 1-propanol (RS) and 280 evaluable product application sites for groin and abdominal regions for the other three study product arms can be achieved.

| Product Combination | No. of Subjects in Each Block |
|---------------------|-------------------------------|
| A-B | 16 |
| A-C | 27 |
| A-D | 27 |
| B-C | 16 |
| B-D | 16 |
| C-D | 27 |
| Total | 129 |

Left/Right Balance

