4.0 STUDY POPULATION

Healthy male and female volunteers, 18 years of age or older, with no dermatological conditions or known history of sensitivity to natural rubber latex, adhesive skin products (e.g., Band-Aids, medical tapes), isopropyl alcohol or chlorhexidine gluconate will be enrolled into this study. A sufficient number of volunteers will be enrolled such that a minimum number of evaluable product application sites are available for the groin (sebaceous rich) region and the abdominal (sebaceous poor) region for each of the study products. A minimum of 280 evaluable sites per anatomical location is required for the IP, AC, and NC. A minimum number of 192 evaluable site per anatomical location is required for the RS.

The minimum number of volunteers enrolled will be 516 based on the objective to assess four study product arms on the required number of unique skin sites for the groin and abdomen. Subjects must satisfy all Screening Day and Product Application Day Inclusion/Exclusion Criteria prior to Product Application Day procedures.

Subjects must qualify on all four abdomen and inguinal sites to be admitted into the study until such time that one of the anatomical sites has completed the minimal required evaluable sites, then subjects will be screened and treated on the remaining anatomical site. To be included in the primary analysis (modified Intent to Treat (mITT) data set), a product application site must have a Product Application Day microbial baseline within the stated requirements. Enrollment will continue until a minimum number of subjects meeting baseline criteria on each anatomical site per study product arm is identified.

Subjects will be treated utilizing bilateral applications to ensure that the study products will be evaluated on the sites as described in Table . Each subject has four independent product application sites: left and right sides for the abdomen and left and right sides for the groin.

| Arm | Study Product | Number of Abdomen Evaluations | Number of Groin Evaluations |
|-------------------------|---|--------------------------------------|------------------------------------|
| Investigational Product | Single Swabstick impregnated with 2% (w/v) chlorhexidine gluconate (CHG) in 70% (v/v) isopropyl alcohol | 280 | 280 |
| Reference Standard | 60% 1-propanol applied with a single Swabstick | 192 | 192 |
| Negative Control | 0.9% normal saline applied with a single Swabstick | 280 | 280 |

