13.2 Adjustments for Multiple Objectives

An overall significance level of 0.05 ($\alpha = 0.05$) will be used.

This study has two sets of objectives, one for Health Canada analysis and the other for US FDA analysis. These two sets of objectives are considered independently of each other and no alpha adjustments between two sets of objectives are performed.

Within the HC analysis primary objectives, since the study HC efficacy analysis will declare success when and only when all four primary endpoints pass HC analysis acceptance criteria, no multiplicity adjustment is required⁹.

Within the FDA efficacy analysis, a gatekeeping procedure will be applied: the efficacy analysis for two secondary objectives [30-second (abdomen only) post-product application time point] will be performed only when all four primary objectives [10-minute (abdomen and groin) post-product application time point] pass the acceptance criteria. No alpha adjustments between primary and secondary endpoints are performed. For primary objectives [10-minute (abdomen and groin) post-product application time point], since it will declare success when and only when all four primary objectives pass FDA analysis acceptance criteria, no multiplicity adjustment for the four primary objectives is required⁹. For secondary objectives [30-second (abdomen only) post-product application time point], since it will declare success when and only when all four primary and two secondary objectives pass FDA analysis acceptance criteria, no multiplicity adjustment for the two secondary endpoints is required⁹.

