Table A.3.3: mITT/PP - Summary Statistics for FDA Analysis - Responder Rate at 6 Hours

Body Location	Product	Responder Rate
Abdomen/Groin	IP/AC/NC	n/N (%)

Note: n is number of responders and N is total number of evaluable subjects.

Table A.3.4: mITT/PP - Summary Statistics for FDA Analysis - Product Weight

Body Location	Product	Count	Mean	Median	SD	Range (Min-Max)
Abdomen/Groin	IP/AC/NC	n	x.xx	x.xx	x.xx	x.xx - x.xx

Table A.3.5: mITT/PP - Analysis Results for FDA Analysis - ATE at 10 Minutes

Body Location	Contrast	Time Point	ATE (95% CI)	Met Criteria
Abdomen/Groin	IP-AC	10 Minutes	x.xx (x.xx, x.xx)	Yes/No
Abdomen/Groin	NC-IP	10 Minutes	x.xx (x.xx, x.xx)	Yes/No

Table A.3.6: mITT/PP - Analysis Results for for FDA Analysis - ATE at 30 Seconds

Body Location	Contrast	Time Point	ATE (95% CI)	Met Criteria
Abdomen	IP-AC	30 Seconds	x.xx (x.xx, x.xx)	Yes/No
Abdomen	NC-IP	30 Seconds	x.xx (x.xx, x.xx)	Yes/No

A.4 Safety Analysis

Table A.4.1: ITT - Summary Statistics for Irritation Scores for Abdomen/Groin at Baseline/30 Seconds/10 Minutes/6 Hours

Characteristic	IP	RS	AC	NC	Overall
Erythema					
0-No reaction	n (%)	n (%)	n (%)	n (%)	n (%)
1-Mild and/or transient redness	n (%)	n (%)	n (%)	n (%)	n (%)
2-Moderate redness	n (%)	n (%)	n (%)	n (%)	n (%)
3-Severe redness	n (%)	n (%)	n (%)	n (%)	n (%)
Edema					
0-No reaction	n (%)	n (%)	n (%)	n (%)	n (%)
1-Mild and/or transient swelling	n (%)	n (%)	n (%)	n (%)	n (%)
2-Moderate swelling	n (%)	n (%)	n (%)	n (%)	n (%)
3-Severe swelling	n (%)	n (%)	n (%)	n (%)	n (%)
Rash					
0-No reaction	n (%)	n (%)	n (%)	n (%)	n (%)
1-Mild and/or transient rash	n (%)	n (%)	n (%)	n (%)	n (%)
2-Moderate rash	n (%)	n (%)	n (%)	n (%)	n (%)
3-Severe rash	n (%)	n (%)	n (%)	n (%)	n (%)
Dryness					
0-No reaction	n (%)	n (%)	n (%)	n (%)	n (%)
1-Mild and/or transient dryness	n (%)	n (%)	n (%)	n (%)	n (%)
2-Moderate dryness	n (%)	n (%)	n (%)	n (%)	n (%)
3-Severe dryness	n (%)	n (%)	n (%)	n (%)	n (%)

Table A.4.2: ITT - Adverse Events Summary

Characteristic	IP	RS	AC	NC	Overall
Adverse Events					
No	n (%)	n (%)	n (%)	n (%)	n (%)
Yes	n (%)	n (%)	n (%)	n (%)	n (%)

Note: Overall column is calculated based on overall unique subjects included in ITT.

Table A.4.3: ITT - Safety Analysis - Overall Comparisons for Erythema/Edema/Rash/Dryness

Body Location	Time Point	p-value	Conclusion
Abdomen/Groin	30 Seconds	0.xxx	Sign. Diff/No Sign. Diff
Abdomen/Groin	10 Minutes	0.xxx	Sign. Diff/No Sign. Diff
Abdomen/Groin	6 Hours	0.xxx	Sign. Diff/No Sign. Diff

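### The Fisher test on skin irritation ignores that each subject carries two products; if left and right reactions are positively correlated, it runs below its nominal 5% and loses some power

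*Protocol*

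**What the plan says.** Protocol summary (Safety Analysis), Protocol 13.5.6 and SAP 6.2.3 all specify the same test: "The statistical significance of differences in skin irritation between the study products at each post application sampling time will be evaluated by Fisher"'s exact test. The outcome is binary, with "any reaction above a zero (no reaction) on the skin irritation rating scale for any category" counted as positive. The population is broad: "The full intent-to-treat (ITT) data set (all randomized subjects that received study product) will be used for the safety analysis".

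Protocol 3.3.1 sets the design: "Each subject will receive two different study products, one on the right side of the body and one on the left". Its block table fixes how many subjects receive each of the six product combinations. Protocol 4.0 says "Each subject has four independent product application sites". Neither document gives the irritation test a paired, stratified or clustered form.

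SAP Table A.4.3 reports one conclusion per body location and time, "Sign. Diff/No Sign. Diff". A significant result opens follow-up comparisons (SAP Table A.4.4). These will be done according to the protocol and may be done according to the SAP. Adverse events get no inferential analysis, so this is the only planned inferential safety comparison.

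**The concern.** Fisher's test on a product-by-reaction table derives its null distribution as if each site came from a different person. Here each person supplies two sites per body region, always under different products. A person with reactive skin may score above zero on both sides. The two sides share the same subject, clipping where required, the period without bathing, scrub-cup sampling and the dressing until 6 hours, so a positive correlation is plausible.

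When correlated observations fall in different product groups, the difference between products varies less than the test assumes, and p-values come out too large. In an efficacy claim that would be hard on the product. In a safety comparison it tilts the label towards no significant difference and makes the follow-up comparisons less likely to be run. The bilateral design supplies a within-person contrast that the planned test does not use.

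**Working it through.** **Inputs from the documents.** Subjects per block for A-B, A-C, A-D, B-C, B-D, C-D: 16, 27, 27, 16, 16, 27, with four blocks and B = RS (Protocol 3.3.1). Nominal level 0.05; Protocol 13.2 sets "An overall significance level of 0.05" and gives the irritation test no level of its own.

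**Inputs that are assumed.** Reaction rates and the left-right correlation ρ of the 0/1 outcome. Neither document gives them.

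**1. Allocation.** Four blocks give 64, 108, 108, 64, 64 and 108 subjects, total 516. Sites per region: A = 64 + 108 + 108 = 280; B = 64 + 64 + 64 = 192; C and D = 280 each. This matches the plan. The table holds 1,032 sites from 516 people.

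**2. Two products, IP against AC.** With common rate p, independent sites would give variance 2p(1 − p)/280. The 108 shared subjects change it to

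Var = [2p(1 − p)/280] × [1 − (108/280)ρ] = [2p(1 − p)/280] × (1 − 0.386ρ).

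The true level of a nominal two-sided 5% comparison is 2Φ(−1.96/√(1 − 0.386ρ)): 4.1% at ρ = 0.2, 2.9% at 0.5 and 1.8% at 0.8.

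**3. All four products (3 degrees of freedom).** The same covariance multiplies two of the three components by 1 − (108/280)ρ and the third by 1 − (64/280)ρ. At ρ = 0.5 these are 0.807, 0.807 and 0.886. Comparing the resulting statistic with the chi-square cut-off 7.81 gives the large-sample column below. The simulated column is the 4 × 2 Fisher test on the exact allocation, 8,000 null trials per setting, reaction rates 1–30%.

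| ρ (0/1 outcome) | Large-sample level | Simulated level |
|---|---|---|
| 0 | 5.0% | 4.8–5.0% |
| 0.2 | 3.9% | 3.5–4.0% |
| 0.3 | 3.4% | 3.0–3.7% |
| 0.5 | 2.5% | 2.3–2.8% |
| 0.7 | 1.7% | 1.5–1.9% |

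At ρ = 0 the nominal 5% is reproduced, so at rates of 1% or more the shortfall comes from the ignored pairing, not from the discreteness of the exact test.

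**4. Rare reactions.** The table fixes ρ on the 0/1 scale. If a shared tendency acts on an underlying normal scale, the 0/1 correlation shrinks as reactions become rare. With underlying correlation 0.3–0.5 (0/1 correlation 0.05–0.20), Fisher's level was 4.5–4.8% at a 1% rate, 4.4–4.9% at 2% and 3.9–4.8% at 5%. At underlying correlation 0.7 it was 3.0–3.8%.

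**5. Power.** For one product at 10% and the others at 5%, Fisher against a 3-df test using the within-person covariance gave 64% against 66% at ρ = 0, 62% against 69% at 0.20, and 63% against 75% at 0.44. Fisher's own power hardly moves with ρ; the loss is relative to a test that uses the pairing. For the permutation test proposed below, the gain over the pooled test was 4–11 points at ρ of 0.2–0.5 (10% against 5%, and 28% against 20%). At zero correlation both had 64%. Its level stayed within simulation error of 5% or below.

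**The case against.** **The level depends on an unknown correlation.** This stands. A reader might infer that the test does run at 2–4%; the documents do not support that, because they give no correlation and no reaction rate. With uncorrelated sides the level is 5%.

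**Reactions may be rare.** Subjects are healthy, any score of 1 or more before application excludes, and each product is applied once and followed for 6 hours. The note to SAP Table A.4.3 allows for p-values that are not applicable. Step 4 shows a small shortfall in that setting. This stands as a limit on size, not on the mechanism.

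**The test is not invalid.** Under positive correlation its level stays at or below 5%. A reader used to clustering that inflates false positives might expect the opposite; here the two correlated sites always carry different products, so the effect is conservative. The cost is efficiency.

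**An excess would still be visible.** SAP Table A.4.1 tabulates every irritation score by product, region and time whatever the p-value, adverse events are listed and summarised separately, and safety has no acceptance criterion. This stands and rules out any reading that the test could hide irritation from the report.

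**Several tests are run unadjusted.** Two regions and three times make at least six, so the chance of at least one false signal need not be below 5%. That is true, but it does not restore the lost power of each test.

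**A common remedy can be worse.** A subject-clustered score test with empirical covariance rejected a true null in 9–17% of trials at a 1% rate and about 8% at 2%. Swapping labels only within subjects loses about 4–7 points of power if the sides are uncorrelated. Both objections are fair and determine the choice of remedy.

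**Conclusion.** The point holds conditionally. The planned test assumes an independence between a subject's two sites that the design does not provide. With positive left-right correlation it is conservative: about 5% at correlation 0, about 4% at 0.2–0.3 (3.0–4.0% in the table above) and 2–3% at about 0.5. The power given up is about 4–11 points in the settings examined. These figures rest on assumed rates and correlations and on the minimum 516-subject allocation; they apply to each test separately, and the shortfall is smaller when reactions are rare.

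What is affected is the significance label in SAP Table A.4.3 and the trigger for Table A.4.4. A reader might carry the point over to the efficacy criteria or to the trial's success; it does not bear on either, because no acceptance decision uses this test. The change is worth making because this is the only inferential safety comparison, the error leans towards finding no difference, and a better-calibrated test needs no new data.

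**What to change.** In the protocol summary, Protocol 13.5.6 and SAP 6.2.3, keep the product-by-reaction table but take its p-value, for each region and time, from a permutation test. Hold each subject's two outcomes together and re-randomise the product pair and side among the subjects treated in that region, following the allocation scheme. Fix the test statistic, number of permutations and random seed in advance.

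Do the Table A.4.4 follow-up comparisons the same way, re-randomising only the labels of the two products compared. Any odds-ratio interval computed as if sites were independent should be marked as such. Do not rely on a GEE score test with empirical covariance, because its level may be inflated when reactions are rare.

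Cost: a few sentences, a few lines of R and Monte Carlo p-values. No extra data or subjects are needed and the table layouts can stay. No power loss was seen when the sides are uncorrelated.
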